## Study Outcomes:

- Primary outcomes will be volume of the alveolar ridge at 12 months as measured by 3D intraoral scanning.
- Secondary outcomes will be implant survival, bleeding upon probing, marginal bone levels (MBLs) as measured by peri-apical radiographs and patient satisfaction as measures by the OHIP patient survey.

The research study will be performed at the UIC Dental School Clinical Research Center and will involve multiple clinic visits. These clinic visits usually occur at the same time as the subjects clinic visits for implant therapy, to avoid any research-only visits. The schedule for obtaining a dental implant is shown above in Figure 1 in blue with research visits shown in green and is described below:

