### 1. First visit: ("Screening/Enrollment")

Subject screening, enrollment and the informed consent discussion will occur at this visit. Upon obtaining consent, medical and dental history may also be obtained from subjects. A scanned image of the subjects jaw bones, called a "cone beam CT" (CBCT) in addition to a 3D intraoral scan, will be obtained for the purpose of standard of care. This visit will require 30 - 60 minutes.

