### 6. Sixth visit: ("1 year follow-up")

This final visit will be approximately 1 year post-surgical followup and is performed in accordance with standard of care. Additionally, a 3D intraoral scan will be performed, subject will be asked to complete the OHIP patient satisfaction questionnaire and will receive a \$50 gift card for research purposes.

This visit will require approximately 30 – 60 minutes. Should any complication be observed at this time, appropriate standard of care interventions will be made at that time and the subject will be referred to the UIC College of Dentistry dental clinics or their dentist for further treatment or retreatment.

All 3D intraoral scans are light-based, are not x-ray scans, and utilize scanners sold to and used by dentists in replacement of conventional impressions

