## **7.0 Expected Risks/Benefits**

The risks of dental implant therapy are minimal but include complications such as bleeding and bruising after surgery, post-surgical pain, infection, delayed healing, temporary speech problems, bone fracture, temporary or permanent damage to the nerves of the jaw, loss of bone on the upper or lower jaw (including altered appearance of the gum line), infection in the bone, damage to the adjacent teeth, chronic pain, abscess, and infection of the gums.

Risks of a PerioDerm® allograft include local or systemic infection, dehiscence (*wound rupture along the line of incision*) and/or necrosis (*death of tissue*) due to poor revascularization or allergic response to some component(s) of the graft material.

In accordance with the graft manufacturer's instructions, tissue recipient records for subjects receiving PerioDerm® will be maintained for the purpose of post-transplant tracing. This may increase the risk to the privacy of subjects randomized to +Graft.

CBCT and other 3D intraoral scanner capture light-generated images which are compiled by the appropriate software into a 3 dimensional geometric image. Since these scanners does not utilize xray technology, the medical risks of use are minimal and include mild fatigue of the facial muscles.

Subjects will be encouraged to contact the PI in the event of medical emergencies related to his/her dental care and will be provided a 24-hour emergency contact number. Subjects experiencing complication may require additional (>5) clinic visits during the course of this study. This is clearly indicated within the consent document.

If implant integration fails or the implant site is infected, the implant will be removed or the site infection treated using standard dental therapies. The subject will be excluded from this study and referred to UIC College of Dentistry for care.

Restoration of the oral cavity is likely to benefit all subjects, irrespective of study group. The potential for an enhanced restoration in the +Graft study group, as compared to the -Graft group, is the focus of this study.

Results from this research may lead to modifications in standards of care which may benefit future patients receiving dental implant therapy.

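### Section 7.0 wrongly describes CBCT as light-based imaging without X-rays, and the rules for removing subjects after implant failure conflict and could take failures out of the implant survival outcome

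*Combined protocol and SAP*

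**What the plan says.** **Imaging.** Under the first visit, section 6.0 describes a cone beam CT as "A scanned image of the subjects jaw bones" and continues: "CBCT) in addition to a 3D intraoral scan, will be obtained for the purpose of standard of care". Under the sixth visit it states: "All 3D intraoral scans are light-based, are not x-ray scans". Section 7.0 puts the two methods together: "CBCT and other 3D intraoral scanner capture light-generated images". It then reasons: "Since these scanners does not utilize xray technology", "the medical risks of use are minimal and include mild fatigue of the facial muscles".

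**Outcomes.** The outcome list in section 6.0 dates the primary outcome: "Primary outcomes will be volume of the alveolar ridge at 12 months". The secondary outcomes are implant survival, "bleeding upon probing, marginal bone levels (MBLs) as measured by peri-apical radiographs", and patient satisfaction by the OHIP survey. The list gives no time for any of these four.

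**Failed implants.** The fourth visit (8 weeks) and fifth visit (10-12 weeks) check integration by touch. If the implant has not integrated, it is removed, and discontinuing the subject is left optional. Section 7.0 states exclusion from the study as definite, for failed integration and also for an infected site. Section 11.2 states dismissal after implant failure as definite.

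**The concern.** The risk section rests its minimal-risk conclusion on the absence of X-rays, although the protocol includes a CT scan and names peri-apical radiographs as the measure of one outcome. A risk statement of this kind is a natural source for consent wording, so an error here could reach subjects.

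Implant survival raises a different problem. The event that defines the outcome also triggers removal from the study. No section says who is in the survival analysis, or that a removed subject still counts in it. If exclusion were carried through to the denominator, the outcome could not register the failures it is meant to count.

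**Working it through.** The plan gives no figure to reproduce on this point. The first and third steps compare the text; the second needs simple arithmetic.

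**1. Imaging statements side by side**

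| Place | CBCT | Intraoral scan | Peri-apical radiographs |
|---|---|---|---|
| 6.0, Study Outcomes | not mentioned | measures the primary outcome | measure marginal bone level |
| 6.0, First visit | cone beam CT of the jaw bones, standard of care | listed separately | not mentioned |
| 6.0, Sixth visit | not mentioned | light-based, no X-rays | not mentioned |
| 7.0 | grouped with light-based scanners, no X-rays | same group | not mentioned |

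The first visit treats CBCT as something other than the intraoral scan, and the sixth visit makes its no-X-ray statement about intraoral scans alone. Section 7.0 extends that statement to CBCT. Computed tomography is an X-ray method, so the extension is false, and the risk conclusion drawn from it has no basis for CBCT.

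**2. Implant survival**

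Inputs: n = 20 per group (section 12.0); f = number of failed implants in a group. The plan gives no failure rate, so f is assumed.

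- Failures counted: (n − f)/n
- Failed subjects left out: (n − f)/(n − f) = 100% for any f below n

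| f | Failures counted | Failed subjects left out |
|---|---|---|
| 1 | 19/20 = 95% | 19/19 = 100% |
| 2 | 18/20 = 90% | 18/18 = 100% |

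Under the second rule each group shows 100% whatever happens. A group with two failures could not be told apart from a group with none.

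**3. Where the secondary measures are placed in the six visit descriptions**

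- OHIP: second visit (before surgery) and sixth visit (about 1 year).
- Integration check: fourth and fifth visits; not named at the sixth.
- Probing: not named at any visit.
- Peri-apical radiographs: not named at any visit.

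Section 6.0 also refers to a schedule figure that is not in our copy. Section 11.2 lists data collection times ending at 12 months but assigns no measure to them.

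**The case against.** **CBCT is standard of care, so the study adds no CBCT exposure, and the consent form cannot be seen.** Both are true. Nothing here shows that subjects were misinformed or exposed to more radiation because of the trial. The sentence in section 7.0 is still incorrect, and the peri-apical radiographs are still missing from that section.

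**Dismissal may only end follow-up.** Failures are looked for at 8 weeks and at 10-12 weeks and are known before the subject leaves. An analyst would hardly drop failures from an outcome called survival. This has force: the documents do not show that anyone intends to leave them out. But section 7.0 speaks of exclusion from the study, no section defines the analysis set, and the removal statements disagree with one another.

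**Stronger readings of the timing gap.** A reader might infer that none of the secondary outcomes has any measurement time, or that probing and radiographs were never scheduled. The documents do not support this. OHIP is placed before surgery and at about 1 year. Twelve months is the natural reading for the others: section 3.0 allots 12 months to treatment and evaluation, the primary outcome is set at 12 months, the 1-year visit is final, and the list in section 11.2 ends there. The schedule figure may list both measures, and the final visit follows standard of care, which may supply the readings. A reader might also infer an inflated false-positive rate from a free choice of visit, or a loss of precision from missing films. Either would need candidate reading times or completion rates that the documents do not give, so no size is put on them.

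**Conclusion.** Two parts hold and one is a clarification.

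1. The CBCT statement in section 7.0 is wrong as written and conflicts with section 6.0. This rests on the text and on the fact that CT uses X-rays. Its importance lies in the safety information; it changes no estimate.
2. The rules for subjects with failed implants are inconsistent and leave the survival denominator open. The size is 95% against 100% for one failure in a group of 20. This assumes one failure and that exclusion is carried through to the analysis, which the text permits but does not state.
3. The missing times for secondary outcomes in the outcome list, and the absence of probing and peri-apical radiographs from the visit text, call for clarification only, subject to what the schedule figure shows.

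The corrections should be made. The primary outcome and its 12-month scan do not depend on them.

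**What to change.** - **Section 7.0:** restrict the light-based, no-X-ray sentence to the intraoral scanner. Describe CBCT (as standard of care) and the peri-apical radiographs as X-ray imaging in the risk text. Check that the consent form agrees.
- **Sections 6.0, 7.0 and 11.2:** reconcile the statements on what happens to a subject after implant failure. Whichever clinical handling is kept, state that every randomised subject who received an implant stays in the survival analysis at 12 months, with implants removed before then counted as failures.
- **Clarification:** state the analysis time for the secondary outcomes. If the schedule figure does not already place probing and the peri-apical radiograph, name both at the 1-year visit. For OHIP, say whether the endpoint is the 1-year score or the change from before surgery.

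Cost: one protocol amendment with IRB review and a consent form check. Counting removed implants as failures found at the fourth and fifth visits needs no new data. If the probing and radiograph are not already part of the 1-year visit, add a few minutes of chair time and one film per subject (40 × 1 = 40 films), each with a small radiation exposure that the corrected section 7.0 would disclose.

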#### **6.0 Study Design and Procedures**

This will be a randomized interventional study of PerioDerm® gum allograft (“+Graft”) plus standard dental implant with crown therapy versus standard dental implant with crown therapy alone (“-Graft”).

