### 2. Second visit: ("Implant surgery")

The second visit will be coordinated with usual and customary treatment for dental implant therapy. Prior to implant surgery, subject will be asked to complete the OHIP patient satisfaction questionnaire. This questionnaire is for research purposes only. Additionally, at the second visit, subjects will be randomized (+Graft vs. -Graft) by authorized study personnel and his/her implant, with abutment and temporary crown, will be placed (+/- Graft). The abutment and temporary crown will be placed onto the implant. If this implant is not stable, a healing abutment will be placed instead and a removable temporary will be provided within 24 hours. The experimental variable in this study is placement of a submucosal allograft in randomized patients. PerioDerm® is not an

experimental material and is available for sale and use within the USA (see Appendix A1). This visit will require approximately 2 hours.

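### No masking of subjects is described, so a 1-year OHIP difference favouring the graft could partly reflect knowledge of the allocation

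*Combined protocol and SAP*

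**What the plan says.** Section 6.0 gives the design as "This will be a randomized interventional study of PerioDerm® gum allograft" with standard implant and crown therapy, "versus standard dental implant with crown therapy alone". Neither phrase carries a masking term, and no sham or placebo graft is described for the comparator.

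Under Study Outcomes, the primary is stated as "Primary outcomes will be volume of the alveolar ridge at 12 months as measured by 3D intraoral scanning". The secondary outcomes are implant survival, bleeding on probing, marginal bone level on radiographs, and "patient satisfaction as measures by the OHIP patient survey".

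OHIP is collected twice. At the second visit: "Prior to implant surgery, subject will be asked to complete the OHIP patient satisfaction questionnaire". At the sixth visit, about a year after surgery, "subject will be asked to complete the OHIP patient satisfaction questionnaire" again.

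Allocation also takes place at the second visit, where "subjects will be randomized (+Graft vs. -Graft) by authorized study personnel". The text does not say whether the subject learns the result, or whether the baseline questionnaire comes before or after that step.

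**The concern.** For OHIP the subject is the assessor. Sections 3.0 and 7.0 present the trial as a test of whether the graft gives a better restoration. Section 11.2 says that the anticipated adverse events, which include those of the graft, are described in the consent document. Subjects will therefore know that the graft is the thing being tested. A subject who also learns the arm has up to a year with that knowledge before scoring satisfaction.

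At stake is the patient's view of the result. The aims cover appearance as well as health, and OHIP is the only listed outcome that records the subject's own judgement. A claim of benefit as patients see it would rest on this comparison.

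**Working it through.** The plan states no figure for OHIP, so there is none to reproduce. The check is a reading of the text, followed by an illustration under stated assumptions.

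**1. Is masking described anywhere?** Section 6.0, where a masking procedure would belong, is available from the design statement through all six visits. Neither it nor any other supplied section mentions blinding, a sham, withholding of the arm, or a question on perceived allocation. No section says that subjects are told their arm.

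**2. Which outcomes depend on the subject's answers?** Ridge volume comes from a scan, marginal bone level from a radiograph, and bleeding and survival from clinical examination. Only OHIP is self-reported.

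**3. Does the baseline OHIP protect the comparison?** Code scores so that a positive difference favours +Graft. Let T be the true effect on the 1-year score, and let R(+) and R(-) be the mean shifts in that score caused by knowing the arm. Then

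expected 1-year difference = T + [R(+) - R(-)].

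Adjusting for a baseline score taken before allocation removes chance imbalance and reduces variance, but it leaves the bracket untouched. If the baseline is answered after the arm is known, which the second-visit text does not exclude, the baseline may carry a shift of its own.

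**4. Is masking feasible?** Section 2.0 describes a submucosal graft placed immediately after the implant. Section 6.0 puts both in the same surgical visit and gives one visit schedule for all subjects. Section 1.0 notes that the allograft avoids taking tissue from the palate, so no donor wound reveals the arm.

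**5. Illustration.** Inputs: 20 per group (Section 12.0). Assumptions, not from the documents: T = 0, two-sided 5% test, normal approximation, and a net reporting shift of b standard deviations. With L = b / sqrt(2/20) = b / 0.316,

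probability of a significant difference = Phi(L - 1.96) + Phi(-L - 1.96).

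| b (assumed) | L | Probability |
|---|---|---|
| 0 | 0 | 5.0% |
| 0.2 | 0.632 | 9.7% |
| 0.3 | 0.949 | 15.8% |
| 0.5 | 1.581 | 35.3% |
| 0.8 | 2.530 | 71.6% |

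For b above zero, nearly all of this probability favours +Graft (9.2% of the 9.7% at b = 0.2). If only a fraction p of subjects in each arm know their allocation, the shift is p times b: with p = 0.5 and b = 0.5 it is 0.25, between the second and third rows. The table shows how a shift would act. It does not estimate one.

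**The case against.** The strongest objection is that silence is not disclosure. A reader might infer that the trial is open-label and that subjects are told their arm. The documents do not say so, and what subjects are told could be set out in the consent pages, which were not available. This stands, and it limits the point to saying that no masking is described. It does not remove the point, because nothing in the visit procedures prevents disclosure.

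Second, expectation may be modest. Both arms receive an implant and crown, Section 7.0 expects all subjects to benefit, and Section 1.0 calls the evidence for the graft limited. This also stands: a reader might infer that any OHIP difference would be expectation alone, but the documents support only that it could be so in part.

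Third, masking may fail. Section 7.0 keeps tissue-tracing records for graft recipients only, Section 11.2 allows a clinician outside the research team to manage complications, and Section 12.0 anticipates 1.0 to 1.5 mm of augmentation, which a subject might notice. These are fair limits. Keeping a tracing record does not require telling the subject, however, and a perceived-allocation question would show how far masking held.

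Fourth, OHIP is one of four secondary outcomes, and neither Section 9.0 nor Section 12.0 rests a confirmatory claim on it. This stands and sets the weight of the point.

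**Conclusion.** The point holds as a limit on one secondary outcome. No subject masking is described and OHIP is scored by the subject, so a 1-year difference favouring +Graft could partly reflect knowledge of the allocation. This assumes that at least some subjects learn their arm, which the plan neither states nor prevents. The size of the bias is unknown, and the range in the working rests on assumed shifts.

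Three further inferences are not supported:

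- **That the primary result is compromised by this.** The scan volume does not depend on what subjects answer.
- **That the baseline OHIP is safely before randomisation.** The second-visit text places it before surgery only.
- **That a null OHIP result could hide disappointment in the -Graft arm.** Disappointment there would lower -Graft satisfaction and move the comparison towards +Graft. It could produce a null only by offsetting a true effect against the graft, and the documents give no reason to expect one.

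**What to change.** In Section 6.0, Second visit, state that:

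- the baseline OHIP is completed before randomisation;
- study staff do not tell the subject whether a graft was placed until the 1-year OHIP is complete;
- disclosure is allowed at any time for the subject's care or for tissue tracing, and each disclosure is logged with its date on the CRF.

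In Section 6.0, Sixth visit, state that OHIP is completed first, before any discussion of allocation, and is followed by one question on which arm the subject believes they were in.

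If subjects are not to be masked, say so in Section 6.0 and report the OHIP comparison as unmasked and exploratory.

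The cost is protocol and consent wording, a disclosure log and one extra question. No extra visit is needed. Masking may be imperfect, because a subject may notice the surgery or the augmented tissue. The log and the added question would make that visible in the report.

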### 1. First visit: ("Screening/Enrollment")

Subject screening, enrollment and the informed consent discussion will occur at this visit. Upon obtaining consent, medical and dental history may also be obtained from subjects. A scanned image of the subjects jaw bones, called a "cone beam CT" (CBCT) in addition to a 3D intraoral scan, will be obtained for the purpose of standard of care. This visit will require 30 - 60 minutes.

### 2. Second visit: ("Implant surgery")

The second visit will be coordinated with usual and customary treatment for dental implant therapy. Prior to implant surgery, subject will be asked to complete the OHIP patient satisfaction questionnaire. This questionnaire is for research purposes only. Additionally, at the second visit, subjects will be randomized (+Graft vs. -Graft) by authorized study personnel and his/her implant, with abutment and temporary crown, will be placed (+/- Graft). The abutment and temporary crown will be placed onto the implant. If this implant is not stable, a healing abutment will be placed instead and a removable temporary will be provided within 24 hours. The experimental variable in this study is placement of a submucosal allograft in randomized patients. PerioDerm® is not an

experimental material and is available for sale and use within the USA (see Appendix A1). This visit will require approximately 2 hours.

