## 2.0 Background/Scientific Rationale

An alveolar ridge is the part of the jaw bone which immediately surrounds and anchors the tooth socket (“*alveolus*”). Similar to any bone or muscle atrophying when not used, the alveolar ridge will shrink (“*resorb*”) following tooth extraction. The volume of an alveolar ridge can be measured by 3D intraoral scanning, and is used clinically as a metric of oral health.

A **dental implant** is a titanium screw shaped implant placed into the healed alveolar bone or tooth socket following tooth extraction. It replaces the tooth root and supports the crown that is attached to an abutment. The abutment is surrounded by peri-implant mucosa that protects underlying bone and provides esthetic contour for the artificial tooth.

An **abutment** is a titanium or zirconia transmucosal component that is screwed onto the implant and is designed to connect the crown to the implant. A **crown**, also referred to as a “dental cap”, is an artificial tooth generally made with porcelain or surgical grade metals such as gold or titanium.

Osseointegration is the development of a functional and structural connection between the alveolar ridge of the jaw and the dental implant. Implant success requires both sufficient bone volume for osseointegration and sufficient mucosal tissue to protect against biofilm mediated inflammation, assure functional comfort and contribute to dental implant esthetics. Our own research has demonstrated that following dental implant placement in healed ridges or extraction sockets, the alveolar ridge continues to resorb approximately 0.5 to 1.0 mm during the first year of healing [2]. Healed ridges are also often volumetrically deficient, having lost approximately 30% of their horizontal volume following tooth extraction [3].

To account for this loss in peri-implant architecture, peri-implant mucosal bone grafting has been proposed and is currently part of dental implant therapy. Both autogenous grafts (*mucosal connective tissue from the roof of the patient’s own mouth or “palate”*) and allogeneic grafts (*collagen-rich grafts derived from a genetically non-identical human donor*) are used for these purposes, but there is controversy regarding the effectiveness of this supplemental graft during implant treatment [4-7]. Xenograft mucosal materials are grafts from non-human donors. Popular

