### 4.0 Eligibility

The subject population will be:

- a. Patients at the UIC Dental School who desire placement of a dental implant for an already missing tooth or
- b. Patients at the UIC Dental School who desire placement of a dental implant for a tooth that will soon be extracted or
- c. Patients in the community who desire placement of a dental implant for an already missing tooth or for a tooth that will soon be extracted.

Subject eligibility at UIC will be assessed and determined by the UIC PI with assistance from authorized UIC study co-investigators (Co-Is) and coordinators.

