#### **5.0 Subject Enrollment**

Subjects will be screened by the UIC PI, UIC Co-I and/or authorized UIC study personnel at the UIC College of Dentistry Clinical Research Center. Dental AxiUm records may be reviewed for recruitment purposes. Patients attending the UIC Dental Clinic who desire implant therapy will be examined per standard of care; those found eligible for dental implant therapy will also screened for possible study inclusion.

[figure not shown]
Recruitment flyers may be posted on campus and on the websites of both UIC and the Chicago Dental Society. A recruitment email may be periodically be released on the UIC campus listserve. Interested patients will be instructed to contact the College of Dentistry Clinical Research Center (COD-CRC) to set up a screening appointment where the informed consent discussion and confirmation of study eligibility will occur. Target enrollment will be 40 subjects, but up to 60 subjects may be enrolled if needed to account for screening failures.

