## 12.0 Statistical Considerations

A sample size of 40 subjects is based on previous studies. Our previous investigations of peri-implant mucosal levels have demonstrated that it is possible to distinguish differences of 0.5 mm among groups of 25 subjects. Here, we anticipate augmentation of approximately 1.0 mm – 1.5 mm and should readily determine significant differences between 20 subjects / group. A recent prospective clinical study comparing no graft to a autogenous connective tissue graft demonstrated a significant difference with 20 subjects / group [12]. This study utilized a similar set of inclusion/exclusion criteria and performed a similar intervention. Even a smaller study comparing 8 subjects with grafts to 10 without demonstrated significant 3D volume changes using a similar scanner-based analytic method [13]

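### The allocation method is not described and is not stratified by site type, and no planned analysis would make up for a chance imbalance in site type between two arms of about 20.

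*Combined protocol and SAP*

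**What the plan says.** Section 6.0 calls the trial randomised ("This will be a randomized interventional study of PerioDerm® gum allograft") and its second-visit paragraph adds that "subjects will be randomized (+Graft vs. -Graft) by authorized study personnel". Neither place, nor any other, states a ratio, how the sequence is generated, whether it is blocked or stratified, or how it is concealed. A 1:1 ratio is only implied, by section 12.0, which says the trial "should readily determine significant differences between 20 subjects / group". Section 5.0 sets the number: "Target enrollment will be 40 subjects, but up to 60 subjects may be enrolled if needed to account for screening failures".

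Section 4.0 admits subjects whose tooth is already gone and also "Patients at the UIC Dental School who desire placement of a dental implant for a tooth that will soon be extracted", with community patients of either kind. Section 2.0 describes healed ridges as often deficient, "having lost approximately 30% of their horizontal volume following tooth extraction". It gives first-year resorption after implant placement as one range, 0.5 to 1.0 mm, for healed ridges and extraction sockets together.

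Under Study Outcomes, the primary outcome is the 12-month alveolar ridge volume from 3D intraoral scanning, not a change from baseline. Section 9.0 names software but no model or covariates. Section 12.0 states the planned effect in millimetres: "Here, we anticipate augmentation of approximately 1.0 mm – 1.5 mm".

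**The concern.** If ridges that healed before entry start smaller than ridges where the tooth is still present, and the outcome is the absolute volume a year later, site type carries information about the outcome whatever the graft does. A chance excess of one type in one arm would then look like a graft effect or hide one. In a large trial this averages out. With about 20 per arm, sizeable imbalances are common, and here neither the allocation nor the analysis limits them. Site type can be recorded at screening, before randomisation at the second visit, so it is available as a stratum. Balance cannot be restored once subjects have been allocated.

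**Working it through.** **1. The plan's own figure.** Section 12.0 gives 20 per group with no SD, alpha or power, so it cannot be reproduced. Its only precision statement is that "it is possible to distinguish differences of 0.5 mm among groups of 25 subjects". Assuming two-sided alpha 0.05 and the normal approximation, SD = 0.5 × √(25/2) / (z for alpha + z for power), which is 1.768/2.80 = 0.63 mm at 80% power and 1.768/3.24 = 0.55 mm at 90%. This SD concerns mucosal levels, not ridge volume. The imbalance calculation below does not use it.

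**2. Inputs for the imbalance.** N = 40 (section 5.0) and 20 per arm (section 12.0). The mix of site types is not stated; I assume K = 20 (even) or K = 12 (30%) subjects of one type.

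**3. Chance of a difference in share of 0.20 or more.** Because the method is not stated, two models are shown.
- Arms fixed at 20/20: the number X of that type in one arm is hypergeometric(40, K, 20), and the difference in share is (2X − K)/20. For K = 20, a difference of 0.20 or more means X ≤ 8 or X ≥ 12: 2 × (0.1151 + 0.0436 + 0.0109 + 0.0017 + 0.0002) = 0.343.
- Coin toss for each subject: each of the 40 is assigned with probability 1/2, and the shares are compared over the arm sizes that result.

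| Assumed mix | Arms fixed 20/20 | Coin toss |
|---|---|---|
| Even (K = 20) | 34.3% | 26.8% |
| 30% (K = 12) | 30.1% | 18.7% |

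These count imbalance in either direction; one named direction is half as likely.

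**4. Shift in the unadjusted result.** Shift = difference in share × D, where D is the mean outcome difference between site types. The protocol does not give D. With arms fixed and K = 20, the SD of X is √(20 × 0.5 × 0.5 × 20/39) = 1.60, so the SD of the difference in share is 2 × 1.60/20 = 0.16. Chance imbalance therefore adds a component with SD 0.16 × D to the arm difference (0.15 × D for K = 12).

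**5. What D would have to be.** At a 0.20 difference in share, a shift of one third of the planned effect needs D ≥ 0.333/0.20 = 1.67 mm for a 1.0 mm effect, or 0.50/0.20 = 2.5 mm for 1.5 mm. The chance of a shift that large, at an even mix (fixed arms / coin toss), is:

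| D (assumed) | 1.0 mm effect | 1.5 mm effect |
|---|---|---|
| 1.0 mm | 2.6% / 3.9% | 0.4% / 0.2% |
| 2.0 mm | 34.3% / 27.7% | 11.3% / 15.4% |
| 2.5 mm | 34.3% / 43.0% | 34.3% / 26.8% |

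At D = 0.5 mm the chance is practically zero. If 30% is applied to an assumed intact ridge of 6, 8 or 10 mm, D is 1.8, 2.4 or 3.0 mm, and a 12 vs 8 split shifts the result by 0.36, 0.48 or 0.60 mm. That is 36%, 48% or 60% of 1.0 mm, but 24%, 32% or 40% of 1.5 mm.

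**6. After stratified blocks.** With blocks of 4, each stratum ends at most 2 subjects out of balance and the difference in share is at most 0.10. With blocks of 4 and 6, each stratum is at most 3 out. The worst case among 40 is opposite imbalances in the two strata, for example 11 vs 8 of one type and 9 vs 12 of the other, giving 11/20 − 8/20 = 0.15. A difference of 0.20 cannot then occur, whatever D is.

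**The case against.** The strongest case against is that little harm is shown. Chance imbalance under proper randomisation is not bias: it is part of the standard error and type I error is preserved. Unequal arms matter little: a 15/25 split is worth 2 × 15 × 25/40 = 18.75 per arm, a standard error about 3% wider. If the SD in step 1 applied, 20 per arm would give over 99% power for 1.0 mm, leaving room for some loss. A baseline 3D scan is taken at the first visit, and adjusting for it could absorb much of any site difference. All of this stands except the last point as a defence, because no such adjustment is planned, and the SD belongs to another measure.

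A reader might also infer more than the documents support:
- That allocation is unrestricted. The protocol is silent, and 20 per group suggests that equal arms are intended.
- That about one trial in three would be shifted by a third or more of the planned effect. This needs a site difference of at least 1.67 to 2.5 mm, which is nowhere given. The 30% compares healed ridges with their state before extraction; it does not compare the eligible site types at 12 months. The criteria requiring enough bone without augmentation would narrow the gap, and the protocol does not say whether implants go into fresh sockets. The planned effect is also in mm while the outcome is a volume.
- That site type is the strongest driver of the outcome. No site-specific 12-month result is reported.

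**Conclusion.** The concern holds in a limited form. Allocation is not described, it is not stratified by site type, and the analysis has no planned adjustment, although the protocol's own background gives reason to expect ridge volume to differ by site type. A difference in share of 0.20 or more would arise in about 27-34% of trials at an even mix and about 19-30% at a 30% mix. The ranges reflect the two allocation models, and both mixes are assumptions. The effect on the result cannot be sized from the documents: it scales with an unstated site-type difference and ranges from negligible at 0.5 mm to substantial at 2 mm or more. What is lost is precision and credibility; the estimate is not systematically biased. The case for the change does not depend on the true difference, because stratified blocking limits the imbalance whatever it is.

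**What to change.** In section 6.0, second visit, state: 1:1 allocation from a computer-generated list prepared before first enrolment, stratified by site type (tooth already missing or tooth to be extracted, as recorded at screening), in permuted blocks of randomly varying size such as 4 and 6. Avoid blocks of 2: staff at a single centre who know earlier assignments could predict the next one too often. State also that each assignment is concealed from enrolling and surgical staff until it is made, for example by sealed opaque envelopes or a locked electronic list.

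In section 9.0 or 12.0, state that the primary comparison includes site type as a factor and adjusts for volume on the 3D scan already taken at the first visit. Both terms are worth keeping: the protocol does not say whether a tooth awaiting extraction is still present at that scan, so baseline volume may not mean the same thing in the two site types.

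The cost is a few sentences, a short program for the list and one or two degrees of freedom, with no extra visit or procedure. Blocking leaves slight predictability, which concealment and varying block size limit. The change must be in place before the first subject is randomised.
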